The identification of NAC as potential treatments for youth CUD is an important development, but to optimize translation to real-world practice and enhance youth CUD outcomes, this trial is critical. At present, it is unclear whether NAC requires a CM platform for efficacy, and regardless of psychosocial/behavioral treatment platform, the initial positive trial of NAC requires replication. The proposed study is designed with adequate power to evaluate the effect of NAC versus PBO on cannabis cessation. Further, the trial is positioned, regardless of between-group efficacy outcomes, to carefully examine potential cognitive task performance improvement with early abstinence achieved during treatment. Given the clear demonstration of potentially lasting adverse cognitive effects of frequent youth cannabis use, and given the central role of learning and academic achievement in this developmental phase, it is important to assess what domains of cognition may acutely improve during successful cannabis cessation treatment engagement.

This proposed trial is the clear “next step” in the assessment of NAC as a youth CUD treatment, and is positioned to inform researchers, clinicians, and the general public, addressing a critical need for optimization of youth CUD treatment.

BACKGROUND – Research Strategy

A. SIGNIFICANCE

Youth Cannabis Use: Prevalence and Implications

Youth are more likely than adults to initiate cannabis use, develop cannabis use disorder (CUD), and suffer potentially lasting adverse consequences of use (1,2). Amid evolving cannabis-related policies in the United States (e.g., state-level legalization for medical and recreational use), youth perceptions of cannabis-related harms are decreasing and rates of use are increasing. Currently, 44% of high school seniors have tried cannabis, 21% are current users, and 6% use daily (3).

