Treatment development for youth CUD has, to date, focused almost exclusively on psychosocial treatments. Trials of motivational enhancement therapy, cognitive-behavioral therapy, community reinforcement therapy, and family therapy have revealed similarly modest outcomes, with very few youth achieving sustained abstinence (24-27), echoing results in the larger literature involving psychosocial treatments for youth substance use in general (28,29). The behavioral treatment contingency management (CM) may improve outcomes when added to psychosocial treatments, but it has not consistently translated into clinical practice (30-40). Significant efforts

are needed to enhance outcomes for youth with CUD, and development and refinement of new approaches is critical.

The Potential Role of Pharmacotherapy: N-Acetylcysteine

In the last decade, efforts to develop potential pharmacotherapies for CUD have expanded, though nearly all of this work has focused solely on adult cannabis users (41). Several human laboratory studies have been conducted to screen for medication effects on cannabis craving, withdrawal symptoms, and self-administration, yielding mixed results (42-53). A smaller number of pilot/proof-of-concept randomized controlled trials have been conducted, also yielding mixed results (54-58). Only a handful of trials with adequate power to evaluate intent-to-treat efficacy outcomes have been conducted, and almost all have yielded negative findings (59-61). Among these, only one youth-focused trial of *N*-acetylcysteine (NAC), an *N*-acetyl pro-drug of the naturally occurring amino acid cysteine, has demonstrated statistically significant intent-to-treat positive efficacy findings (62). Youth randomized to receive NAC had more than twice the odds of submitting negative urine cannabinoid tests during treatment than those randomized to receive placebo (see Preliminary Studies below); all participants in that trial received CM, regardless of treatment randomization group. A replication trial (NAC versus placebo, added to CM) in adults was recently completed, with the primary manuscript currently under review for publication (UG1DA013727—CTN0053, PI: Gray) (see Preliminary Studies below) (63).

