The primary study hypothesis was that participants randomized to NAC would have higher odds than those randomized to placebo to submit negative weekly urine cannabinoid tests (UCTs) during treatment. An intent-to-treat (ITT) approach including all randomized participants was used. In all analyses, participants lost to follow up or absent for visits were coded as having a positive UCT at every missed visit.

The proportion of negative UCTs in the NAC and PBO groups at each visit (ITT sample) is shown in the adjoining figure. Though there was no group difference in baseline years of cannabis use, this variable was an independent predictor of positive UCT during treatment ($p=0.007$) and was therefore covaried in the model. Participants randomized to NAC had more than double the odds of negative UCTs during treatment, compared with those randomized to PBO. In the adjusted model, the relationship between treatment and the odds of a negative UCT was $OR=2.4$ (95% CI: 1.1-5.4), $p=0.021$. Through the final treatment visit, 40.9% (190/464) of the UCTs among participants in the NAC group were negative, compared to 27.2%

(126/464) among those in the PBO group, per ITT analysis, assuming any missing urine was positive for cannabinoids. At the post-treatment follow-up visit (four weeks after medication discontinuation), 19.0% (11/58) of the UCTs among participants in the NAC group were negative, compared to 10.3% (6/58) among those in the PBO group. While still numerically favoring NAC, the overall treatment effect lost statistical significance at post-treatment follow-up ($OR=2.2$ [95% CI: 0.7-6.5], $p=0.155$), though the trial was not powered for this outcome.

Models were examined for the possibility of confounding and effect modification of age, weight, gender, and number of previous cannabis quit attempts. None of the variables tested were significant confounders or effect modifiers (all $p>0.60$).

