Participants in our prior trial of NAC for youth CUD completed serial cognitive task performance assessments, demonstrating improvement in multiple cognitive domains (verbal memory, psychomotor performance) among participants who achieved abstinence during the trial, compared to those who continued using cannabis (23). We plan to utilize the same comprehensive cognitive task battery in the proposed trial, and the enhanced sample size will allow for significantly more power to carefully assess cognitive outcomes with abstinence versus continued use, and to (in exploratory fashion) examine potential relationships between NAC and PBO and cognitive outcomes.

C2. Research Team

[figure not shown]
The investigative team, uniquely experienced with pharmacotherapy trials for youth substance use disorders (SUD), is ideally suited to undertake this study. In addition to having completed prior trials of NAC versus PBO, added to CM, for youth CUD (62) and adult CUD (UG1DA013727—CTN0053), the team has also conducted multiple pharmacotherapy trials targeting youth tobacco use disorder (88, U01 DA031779), and is experienced with serial cognitive task performance assessment within a CUD treatment trial (23). The multidisciplinary team is led by a board-certified child and adolescent psychiatrist with specific expertise in clinical trials targeting youth SUD. Each team member possesses expertise vital to the successful completion of the study.

The study will be conducted at a nationally recognized SUD treatment research center, assuring the ability to efficiently complete the project while maintaining the highest quality of protection of human participants and data integrity.

C3. Design and Methods of Current Proposal

C3a. Overview

We propose a 12-week trial of *N*-acetylcysteine (NAC) for cannabis use disorder (CUD) in youth ($N=192$).

C3b. Participants and Feasibility of Recruitment and Retention

Recruitment Strategies

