This study is powered on the hypothesis that there is a clinically significant difference in proportions of negative urine cannabinoid tests (UCTs) among participants receiving NAC versus PBO.

Our previous findings demonstrated proportions of negative UCTs of 41% with NAC+CM and 27% with PBO+CM, but given that CM is itself a powerful treatment, we anticipate more modest proportions without a CM platform (62). Based on our other prior work using pharmacotherapy without a CM platform, we anticipate the proportion of negative UCTs in the PBO group will be between 6% and 10% (61). Although we have no prior clinical results for estimates of the efficacy of NAC alone, we anticipate that it will be at least as efficacious as CM in the proportion of negative UCTs (~27%), resulting in an overall anticipated effect of NAC versus PBO of 25% vs. 10%. With 12 weekly observations taken on each participant, a conservatively estimated autocorrelation as high as $p=0.90$, and a first order autoregressive covariance pattern, we will have greater than 80% power with two-sided $\alpha=0.05$ to detect the stated difference of 15% in proportions of negative UCTs with 67 participants per treatment group ($n=134$ total). Based on performance of past studies, we anticipate a 30% attrition rate during the study treatment period. The inflated samples size of 96 randomized participants per group ($N=192$ total) will thus provide superior power to detect the stated difference in the main effect of NAC versus placebo in the presence of up to a 30% attrition rate.

Based on our previous research we anticipate approximately 25% percent of participants will have negative UCTs at cognitive task performance assessment visits (23). Similarly, our data indicate that negative UCTs were associated with increased verbal memory and psychomotor speed scores at both 4 and 8 weeks during a cannabis cessation trial using NAC + CM versus CM alone (Cohen's $d=0.90$ and $d=0.60$; respectively). The randomized sample size of $N=192$ will provide superior power (99% and 82%, respectively) with an adjusted $\alpha=0.01$, to detect similar effect sizes across cognitive outcome measures taken at mid-treatment, end-of-treatment, and post-treatment follow-up.

Statistical Analysis

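### The 82% power stated for the cognitive aim at d=0.60 needs 25% of all 192 randomized participants to be abstinent and assessed; the plan's own abstinence and attrition inputs give about 65–72%.

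*Combined protocol and SAP*

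**What the plan says.** In C3f, Power and Sample Size, the cognitive aim rests on this assumption: "Based on our previous research we anticipate approximately 25% percent of participants will have negative UCTs at cognitive task performance assessment visits". For N=192 and an adjusted alpha of 0.01, the plan states 99% power at d=0.90 and 82% at d=0.60. It claims this for mid-treatment, end of treatment and post-treatment follow-up.

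The 25% is credited to earlier research. Section C1c ties the same citation to the earlier youth trial: "Participants in our prior trial of NAC for youth CUD completed serial cognitive task performance assessments". Section A, on the role of pharmacotherapy, adds that "all participants in that trial received CM, regardless of treatment randomization group". Section B says that neither arm of the present trial receives CM.

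The preceding paragraph of C3f sets the primary assumptions. It says "given that CM is itself a powerful treatment, we anticipate more modest proportions without a CM platform", puts the placebo rate at 6–10%, and describes its planning figures as "resulting in an overall anticipated effect of NAC versus PBO of 25% vs. 10" percent. It also expects 30% attrition during treatment.

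The Objectives/Specific Aims section says that "the trial is positioned, regardless of between-group efficacy outcomes, to carefully examine potential cognitive task performance improvement" with early abstinence.

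**The concern.** Aim 2 compares participants who are abstinent at a visit with those who are not, so its power depends heavily on the size of the smaller, abstinent group. The plan carries a 25% share over from a trial with CM. One paragraph earlier it argues that rates will be lower without CM, and it gives arm-specific rates that average well below 25%. With placebo at 10%, a 25% overall share would need NAC at 2 × 25 − 10 = 40%. That is close to the 40.9% seen with NAC plus CM (C1a), a level the plan says not to expect here. The cognitive calculation also uses all 192 randomized participants, although 30% attrition is planned.

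Aim 2 is one of two specific aims. If its power is overstated, a null cognitive result can look more informative than it is.

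**Working it through.** **Inputs.** From C3f: N=192, alpha 0.01, d=0.90 and 0.60, share 25%, planned rates 25% and 10%, placebo range 6–10%, attrition 30%. Allocation is 1:1 (C3c). C3f does not say whether this alpha is two-sided; two-sided is assumed because it reproduces the stated figures (one-sided gives 89% at d=0.60).

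**Formula.** Two-sample t-test at one visit: noncentrality = d × √(n₁n₂/(n₁+n₂)), n₁+n₂−2 degrees of freedom, power = probability that the noncentral t exceeds the two-sided 1% critical value.

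**The plan's own figure.** 25% of 192 gives 48 against 144. √(48×144/192) = 6.00, so noncentrality at d=0.60 is 3.60 against a critical value of 2.602. Power is 84.0%, and 99.7% at d=0.90. A Wilcoxon approximation (efficiency 0.955) gives 81.9% and 99.6%. The stated 82% and 99% are therefore reproduced with 25% of all 192 and no attrition. The same share of 134 participants gives only 65% at d=0.60.

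**The plan's other inputs.**
- Overall share: (25% + 10%)/2 = 17.5%; 0.175 × 192 = 33.6, about 34.
- Attenders after 30% attrition: 0.70 × 192 = 134.4, about 134; 25% of 134 = 33.5.
- No NAC effect: 10% of 192 = 19.2, about 19; 6% of 192 = 11.5, rounded up to 12.

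| Case | Abstinent / not | Noncentrality, d=0.60 | Power, d=0.60 | Power, d=0.90 |
|---|---|---|---|---|
| As stated | 48 / 144 | 3.60 | 84.0% | 99.7% |
| 17.5% of 192, no attrition | 34 / 158 | 3.17 | 71.6% | 98.4% |
| 25% of 134 attenders | 33.5 / 100.5 | 3.01 | 65.3% | 97.0% |
| No NAC effect, 10% in both arms | 19 / 173 | 2.48 | 45.4% | 86.8% |
| No NAC effect, 6% in both arms | 12 / 180 | 2.01 | 28.1% | 66.1% |

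The d detectable with 82% power is about 0.59 for 48 against 144, 0.67 for 34 against 158, and 0.70 for 34 against 100. In the last row, rounding down to 11 abstinent participants gives 25% instead of 28%.

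**The case against.** **The two shares may be compatible.** The 25% refers to participants at cognitive visits. The 25% and 10% are proportions of weekly tests, and the Statistical Analysis text counts missed visits as non-abstinent. If 17.5% is such an intent-to-treat rate, then 17.5/0.70 = 25.0% of attenders, exactly the stated share. A reader might infer that the two paragraphs flatly contradict each other; the documents do not show that. But on this reading the sample is about 134, and power at d=0.60 is about 65%, so the 82% still fails.

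**Applying both reductions.** A reader might apply 17.5% to the 134 attenders (23.4 abstinent) and report about 51%. If the 17.5% already counts missed visits as non-abstinent, that deducts attrition twice. The documents do not settle this, so the conclusion does not rest on it.

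**The 25% may already be lowered.** The earlier trial's overall rate during treatment was (190+126)/928 = 34.1%, so 25% could be visit-specific or discounted. The plan describes no adjustment, and a further discount by some CM factor would have no basis in the documents.

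**Repeated measures.** The planned mixed models over several visits could gain power. That is fair, but the stated figures match a single-visit calculation, and no within-person correlation is given from which to size a gain.

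**Follow-up.** C1a reports that, four weeks after treatment, "19.0% (11/58) of the UCTs among participants in the NAC group were negative, compared to 10.3% (6/58) among those in the PBO group", or 17/116 = 14.7%. A reader might take this as a ceiling for the last cognitive visit. It counts missing urines as positive and follows an 8-week course with CM, whereas cognitive follow-up here is at week 26. It suggests that the share may be lower still, but fixes no figure.

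**Gain over the earlier trial.** A reader might conclude that C1c's expectation, "the enhanced sample size will allow for significantly more power to carefully assess cognitive outcomes with abstinence versus continued use", is empty because the abstinent groups are of similar size. It is not. At d=0.60 the earlier 116 participants give about 57% (29 against 87, at 25%) or 67% (40 against 76, at 34.1%), against 72% for 34 against 158 here. C1c states no power figure and needs no change.

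**Conclusion.** The concern holds for the 82% at d=0.60. On either reading of the 25%, the plan's own inputs give about 65–72%, a shortfall of roughly 10 to 17 percentage points. The 99% at d=0.90 essentially stands, at 97–98%. The fault lies in an input and its denominator; the arithmetic itself reproduces.

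The 28–45% at d=0.60 (66–87% at d=0.90) belongs to a scenario: NAC has no effect, the planned placebo rate applies to both arms, and everyone is assessed. A reader might infer that the Objectives statement about examining cognition whatever the efficacy result is therefore false. It states no power, so the documents do not support that; it should be read with this limit.

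All figures assume a single-visit comparison of two means with two-sided alpha 0.01.

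**What to change.** In C3f, Power and Sample Size:

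1. Say whether the abstinent share is of all randomized or of assessed participants, and make it consistent with the 25% and 10% planned by arm and with the 30% attrition.
2. Replace 82% at d=0.60 with about 65–72%, or give the d detectable with 82% power, about 0.67–0.70.
3. Add a labelled scenario: if NAC has no effect and 6–10% applies to both arms, power is about 28–45% at d=0.60 and 66–87% at d=0.90. Refer to it from the Objectives/Specific Aims statement.
4. Note that the share at the post-treatment cognitive visit may be lower still.

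This changes wording only. Sample size, which was set by Aim 1, and conduct are unaffected. The cost is a less favourable stated power for Aim 2.

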Study personnel will review daily reports and uploaded medication-taking videos (see C3e. below), and perform pill counts weekly throughout treatment to monitor medication adherence. Medication tolerability and effects will be systematically assessed. Medication supply will be refreshed for ongoing use over the following week. Participants will be encouraged to contact study personnel between visits to address any immediate concerns regarding adverse effects. If a participant experiences intolerable medication-related adverse effects at any point during the study, a dose reduction to 600 mg twice daily may be undertaken. The dosage may be increased back to 1200 mg twice daily at the discretion of the medical clinician. However, if a participant is unable to tolerate the reduced dose, medication will be discontinued, and the participant will continue to complete study visits.

Post-Treatment Follow-Up

Post-treatment follow-up visits will be conducted at approximately 16 weeks and 26 weeks from initial randomization. Should a participant determine to withdraw from ongoing study participation or it is determined by the PI/medical clinicians that the discontinuation is in the best interest for the participant, an Early Termination visit (following the schedule of events for a Week 26 visit) will be completed. If the participant does not wish to return for a final visit, a “phone visit” will be completed to gather basic health and safety details in addition to current cannabis status.

Incidental Visits

Unscheduled Visits/ Meetings – Unforeseen incidents may occur that would require a participant to return to the office or set up a remote meeting outside of the routine schedule of events. Such incidents could include: technological issues with loaned study equipment, medication dispensation if medication becomes lost/damaged, or an AE that requires immediate attention for proper assessment. It is not expected that these brief visits (likely 15 minutes in duration) would occur with any frequency and the majority of study participants would not require the additional meeting/return to the office.

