Pittsburgh Sleep Quality Index	X ^{!△}	X								X					X	X	X
Columbia Suicide Severity Rating Scale	X [!]	X\$								X					X	X	X
Cognitive Task Performance Testing	X#!	X								X					X		X
Substance Self-Report																	
Cannabis and Other Substance Use History	X! ^{!△}																
Cannabis Quantification	X																
TLFB/Substance Use Daily Reports	X%! ^{!△}	X\$	X	X	X	X	X	X	X	X	X	X	X	X	X	X	X
Cannabis Withdrawal Scale	X	X	X	X	X	X	X	X	X	X	X	X	X	X	X	X	X
Marijuana Craving Questionnaire	X	X	X	X	X	X	X	X	X	X	X	X	X	X	X	X	X
Marijuana Problem Scale	X								X						X	X	X
Obsessive Compulsive Drug Use Scale	X								X						X	X	X
Modified Fagerström Tolerance Questionnaire (mFTQ) and/or Penn State Electronic Cigarette Dependence Index	X ^{!△}																
Motivation and Confidence to Quit	X	X															
Lab Samples/Testing																	
Urine drug test (dipstick)	X ^{!△}	X [^]	X	X	X	X	X	X	X	X	X	X	X	X	X	X	X
Urine Cannabinoids & Creatinine assay	X	X	X	X	X	X	X	X	X	X	X	X	X	X	X	X	X
Urine Pregnancy Test [‡]	X [△]	X\$	X*	X*	X*	X*	X*	X*	X	X*	X*	X*	X*	X*	X*	X	
Psychosocial Procedures																	
Medication Adherence Assessment (Pill Count, Daily Reports, and REDCap Video Review)			X	X	X	X	X	X	X	X	X	X	X	X	X	X	
Cessation Counseling/ Medication Management		X	X	X	X	X	X	X	X	X	X	X	X	X	X		
Medication Dispensation		X	X	X	X	X	X	X	X	X	X	X	X	X	X		
Estimated Visit Length (hours) →	2-3	1.5	.75	.75	.75	.75	.75	.75	1.5	.75	.75	.75	.75	.75	1.5	1	1.5

SC=Screening/Assessment, FU=Follow-Up, ET=Early Termination

ø the week 0 visit is the Randomization Visit, ♀ females only, * PRN for safety/precautionary measure, ^ Urine drug test should be performed at screening/baseline and again before randomization to ensure eligibility, \$ should be completed prior to randomization to ensure eligibility. & If week 6 visit is missed, assessments that are only completed at that visit should be performed at the next attended visit, as long as the window for the end-of-treatment (week 12) visit has not yet opened. % These assessments may be performed at the randomization (week 0) visit, as long as they occur prior to randomization to ensure eligibility. # Training/practice cognitive task performance session. ; ^ data sharing of completed protocol procedures from PRO#80921 as a result of screen failure, > at ET if completed during treatment phase of protocol; ^ data sharing of completed protocol procedures from PRO#94743

C3f. Statistical Methods

Power and Sample Size

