Categorical clinical and demographic variables will be assessed by chi-square tests of independence, while continuous variables will be assessed using Student's t -test. In addition to baseline group differences, preliminary analysis of baseline characteristics with cannabis use outcomes of interest will examine significant correlates of abstinence in the study population. Characteristics found to be significantly associated with cannabis use outcomes will be included as covariates in the initial stages of model development. The primary measure of interest will be the proportion of self-reported abstinence confirmed with negative weekly UCTs (< 50 ng/mL) during the 12 weeks of active treatment. The main effect of NAC on negative weekly UCTs will be assessed with a repeated measure logistic regression using a general estimating equations framework (GEE) (126). Models will be computed both unadjusted and adjusted for significant covariates and confounders found in the preliminary analysis. Working correlation structures will be independently compared using the quasi-likelihood under the independence model criterion statistic (127). All randomized participants will be included in the primary analysis (intent-to-treat; ITT) and participants will be deemed non-abstinent at any missed visit (drop-out/loss-to-follow up included). Model based means will be used to construct the pairwise comparisons of groups (NAC versus PBO). In addition to the longitudinal analysis of negative UCT rates during treatment, rates will be compared between treatment groups at each post-treatment follow-up visit using logistic regression models. Similarly, creatinine adjusted cannabinoid levels will be examined between groups over the course of the treatment and at the post-treatment follow-up visits using linear mixed effects models. We will also, in exploratory fashion, examine group differences in other cannabis-related outcomes (e.g., self-reported cannabis use [Timeline Follow-Back], craving [Marijuana Craving Questionnaire], withdrawal [Cannabis Withdrawal Scale], and associated problems [Marijuana Problem Scale]). In distinct models, the effect of co-occurring tobacco use disorder on cannabis cessation outcomes will be examined. The main effect of co-occurring tobacco use

disorder, as well as the interaction between tobacco use disorder and each treatment assignment (NAC and CM), will be added to the primary efficacy model.

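### The 82% power quoted for the cognitive aim (d=0.60) counts all 192 randomized as assessed; at the plan's own 30% attrition it is about 65% or 76% for a single visit

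*Combined protocol and SAP*

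**What the plan says.** In C3f, Power and Sample Size, the primary-aim paragraph states: "Based on performance of past studies, we anticipate a 30% attrition rate during the study treatment period". It raises 134 participants (67 per arm) to 192 so that power for the NAC effect holds "in the presence of up to a 30% attrition rate".

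The next paragraph deals with Specific Aim 2, which compares cognitive scores between participants who are and are not abstinent. About 25% are expected to be abstinent, described as "percent of participants will have negative UCTs at cognitive task performance assessment visits (23" (the trailing number is a citation). Two effect sizes are taken from the prior trial, d=0.90 and d=0.60. The randomized sample of 192 "will provide superior power (99% and 82%, respectively", at an adjusted alpha of 0.01, for measures taken mid-treatment, at end of treatment and at post-treatment follow-up. Attrition is not mentioned, and no method, sidedness or within-person correlation is given for this aim.

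Under Statistical Analysis, the urine outcome has a missing-data rule: "participants will be deemed non-abstinent at any missed visit". The cognitive scores are compared by abstinence status at the post-baseline visits with generalized linear mixed models; no rule fills in a missing score.

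**The concern.** The same section allows for losing 30% of participants when it sizes the primary aim and then counts those participants as assessed in the cognitive aim. The urine outcome can be scored at a missed visit by calling the participant non-abstinent. A cognitive score cannot: someone who does not attend has no test result and drops out of that visit's comparison.

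If 82% is too high, a null result for an effect of d=0.60 would be read as stronger evidence of no difference than it is. The Objectives make this a numbered specific aim, and the text that follows them says the trial can examine it whatever the NAC result.

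**Working it through.** **Inputs.** From C3f, Power and Sample Size: N=192; abstinent share 25%; alpha 0.01; d=0.90 and 0.60; attrition 30% over the treatment period. *Assumption:* two-sided testing, as stated for the primary aim.

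**Formula.** Two-sample t-test: noncentrality = d × √(n1·n2/(n1+n2)), df = n1+n2−2, power from the noncentral t distribution.

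**Step 1: reproduce the plan's figure.** 25% of 192 gives 48 vs 144, and √(48×144/192) = 6.00.
- d=0.60: noncentrality 3.60, power 84.0% (stated 82%).
- d=0.90: noncentrality 5.40, power 99.7% (stated 99%).

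Other readings at N=192 do not match 82% for d=0.60: one-sided alpha 0.01 gives 89%, two-sided alpha 0.05 gives 95%, and an equal 96/96 split gives 94%. An equal 67/67 split gives 80%, but the text names N=192 and a 25% share, which rules it out.

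**Step 2: apply 30% loss.** 192 × 0.70 = 134.4 assessed. The plan does not say what the 25% is a share of, so there are two cases.
- *Case A, 25% of those assessed:* 33.6 vs 100.8.
- *Case B, 25% of all randomized:* missed visits count as positive and every loss is among non-abstinent participants, giving 48 vs 86.4. C1a used this coding in the prior trial ("participants lost to follow up or absent for visits were coded as having a positive UCT at every missed visit"). No case with a 25% share and 30% loss is more favourable to the plan.

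| Loss | Case A, d=0.60 | Case B, d=0.60 | Case A / B, d=0.90 |
|---|---|---|---|
| 0% | 84% | 84% | 99.7% / 99.7% |
| 15% (assumed, e.g. mid-treatment) | 76% (40.8 vs 122.4) | 81% (48 vs 115.2) | 99% / over 99% |
| 30% | 65% (33.6 vs 100.8) | 76% (48 vs 86.4) | 97% / 99% |

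For d=0.60 at 30% loss the noncentrality is 0.60 × √(33.6×100.8/134.4) = 3.01 in Case A and 0.60 × √(48×86.4/134.4) = 3.33 in Case B.

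**Step 3: how much loss does 82% tolerate?** In Case A power falls to 82% at 183.9 assessed, a loss of 4.2%. In Case B it does so at 171.1 assessed (48 vs 123.1), a loss of 10.9%.

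**Step 4: effect detectable with 82% power at 30% loss.** d = 0.70 (Case A) or 0.64 (Case B), against 0.59 with no loss.

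**Step 5: could pooling visits restore 82%?** Averaging three visits multiplies the variance by (1+2r)/3, where r is the within-person correlation. Assume constant abstinence status and full attendance among the 134.4.

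| r | Case A | Case B |
|---|---|---|
| 0.5 | 86% | 93% |
| 0.7 | 77% | 87% |
| 0.9 | 69% | 80% |

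Reaching 82% needs r of about 0.59 or lower (Case A) or 0.83 or lower (Case B).

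**The case against.** **The figure is correct on its stated basis.** The text ties it to the randomized 192, and there it reproduces. That stands: the fault is an attrition assumption not carried over, not a slip in calculation.

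**The planned analysis is a mixed model over three visits, not a single-visit t-test.** This is the strongest point. Pooling gives 69-93% for r from 0.9 to 0.5, which spans 82%. Baseline adjustment could also help: at 30% loss, 82% would need a baseline-outcome correlation of about 0.52 (Case A) or 0.33 (Case B), taking required variance as 1−r². But the plan states neither correlation for this aim and does not specify baseline adjustment, and the single-visit calculation on 192 already lands close to the stated figures.

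**Actual loss may be below 30%.** The plan treats 30% as an upper bound. Under the Study Timetable, "If week 6 visit is missed, assessments that are only completed at that visit should be performed at the next attended visit", provided the week-12 window has not opened. For those leaving the study, "an Early Termination visit (following the schedule of events for a Week 26 visit) will be completed", and that schedule includes the cognitive battery. The 134 therefore fits end of treatment best, and loss elsewhere may differ. From the prior trial, 84% completion (C3b) among the 106 of 116 who took medication (C1a) suggests 0.84 × 106/116 = 77% retained. That is only a rough approximation. At 23% loss, power is about 71% or 79%, still short of 82%.

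**The 25% share is itself uncertain.** It comes from a trial with contingency management. C3f expects 25% vs 10% negative tests without it, averaging 17.5%. At 30% loss that gives about 51% power if 17.5% of those assessed are abstinent. If it is 17.5% of all randomized with only non-abstinent participants lost, the split is again 33.6 vs 100.8 and power is 65%. This widens the gap.

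**Conclusion.** The concern holds, at minor severity. The 82% describes nearly the full randomized sample and is not supported at the 30% attrition expected in the same section. For a single-visit comparison at two-sided alpha 0.01 with about 134 assessed, power for d=0.60 is about 65% or 76%, depending on the denominator of the 25%. The chance of missing a true d=0.60 is then 24-35%, rather than the 18% implied by the stated figure.

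These numbers rest on two-sided testing, a 25% abstinent share and a single visit. The omission of attrition is certain; the exact replacement value is not, because the plan leaves the denominator and method open. Power for d=0.90 remains 97-99%, and the primary aim and N=192 are unaffected.

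**What to change.** Replace the cognitive power sentence with one based on participants who can be assessed, for example: *With about 134 participants assessed (30% loss) and 25% of them abstinent, a single-visit two-group comparison at two-sided alpha 0.01 has about 65% power for d=0.60 and 97% for d=0.90; d of about 0.70 is detectable with 82% power.* If the 25% is meant as a share of all randomized, with losses only among non-abstinent participants, the corresponding figures are 76%, 99% and 0.64. State which denominator applies and keep only that set.

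If the team wants credit for pooling visits or adjusting for baseline, name the method and give the assumed correlation and attendance. Confirm that 25% is still the expected share without contingency management, and recompute if it is not. Repeating the alpha of 0.01 and its sidedness in the cognitive analysis paragraph would be helpful but is optional.

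The cost is wording only: no extra participants or procedures, and no change to the primary aim. The quoted power for this aim becomes less favourable unless the added assumptions support it.
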